10.2.5 Exploratory analyses

10.2.5.1 PK interpretation

Standard PK parameters such as minimum serum concentrations (Cmin) and, accumulation factor, will be derived. The PK parameters will be described by treatment groups to make an initial assessment of dose linearity/proportionality.

Descriptive statistics (mean, standard deviation, median, min, max, variation coefficient) will be performed on CSF and serum concentrations of temelimab and PK parameters. Data will be evaluated by standard summary statistics and additional descriptive methods including individual data listings and plots of individual and group data. Further population PK analysis is envisaged based on the collected data.

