- To determine the pharmacodynamic effects of temelimab on neuroprotection and remyelination based on neuroimaging.

Exploratory objectives:

- To assess the clinical and cognitive effects of temelimab (including physical disability)
- To assess the effect of temelimab on quality of life
- To assess the effects of temelimab on exploratory neuroimaging endpoints associated with neuroprotection and remyelination.
- To assess the effects of temelimab on fluid biomarkers associated to myelin integrity, target and immune function
- To determine the PK characteristics of temelimab following repeated IV administration (including CSF distribution) and immunogenicity

Study design:

This is a randomized, double-blind, placebo-controlled Phase IIa clinical study, assessing safety, tolerability, pharmacodynamic effects and pharmacokinetics of temelimab, administered at three different dose levels (18 mg/kg or 36 mg/kg or 54 mg/kg).

The study will consist of a Screening period of a maximum duration of up to 3 weeks (Days -21 to -1) and a treatment period of 48 weeks. On Day 1 all patients who meet eligibility criteria may be randomized (randomization ratio 1:1:1:1) into:

- the placebo group
- the 18 mg/kg group

Study Code: GNC-401
Version No: 3.0
Version Date: 2020-05-01

- the 36 mg/kg group
- the 54 mg/kg group

When the first eight (8), patients randomized into either placebo, 18, 36 or 54 mg/kg group respectively, have achieved ≥ 2 months (8 weeks) of exposure to IMP, formal review by an independent Data Safety Monitoring Board (DSMB) of all of the available safety data from the study will be performed.

The independent DSMB will meet thereafter every 4 months and review all of the available safety data.

All patients will receive double-blind IV infusions of study drug (temelimab 18 mg/kg, 36 mg/kg, 54 mg/kg or matching placebo), via monthly IV infusions for up to Week 44. All patients will be observed for 6 hours following completion of the first administration of IMP infusion and at least 2 hours following completion of the subsequent IMP infusions (second to twelfth). Intra-patient dose escalation of temelimab is not permitted.

Study population: Patients with RMS who have been treated with rituximab for at least 1 year and who meet inclusion/exclusion criteria.

Number of subjects: 40 patients with RMS will be randomized and enrolled (30 temelimab at three dose levels (18, 36 or 54 mg/kg) and 10 placebo)

Inclusion criteria:

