1. The subject has given written informed consent to participate in the study
2. Current diagnosis of RMS, based on the McDonald 2017 criteria¹
3. Having received treatment with rituximab, as per local clinical routine for at least 12 months prior to the Screening Visit
4. Having received their last dose of rituximab not more than 8 weeks and not less than 4 weeks before Randomization (Study Day 1)
5. Having B-cell count $<$ Lower limit of detection (LLOD) ($<0.01 \times 10^{-9}$ CD19⁺ cells/ L)
6. Having expanded disability status scale (EDSS) 2.5 – 5.5 inclusive at Screening
7. Present clinical worsening in one or more neurological domains as assessed by EDSS, ambulatory function as assessed by 6MWT or T25FW, cognitive functioning as assessed by SDMT or increased need of walking aids or pharmacological/procedures for bowel and bladder functions over the last year.
8. Brain Magnetic resonance imaging (MRI), lesion burden with >9 T2 cerebral lesions (assessed within the last 24 months)
9. Stable clinical presentation of MS for 30 days prior to Screening e.g. no relapse, no acute neurological exacerbation.
10. Age range from 18 to 55 years (both inclusive)
11. Body weight between 40 – 100 kg (both ranges are inclusive)
12. No disease modifying therapies (DMTs) other than rituximab, within 12 months of Screening

Study Code:
Version No:
Version Date:

GNC-401
3.0
2020-05-01

13. No contraindication to Biomarker assessments: brain Magnetic resonance imaging (MRI), blood/serum collection and cerebrospinal fluid (CSF) collection
14. Agreeing to undergo two lumbar puncture
15. Be willing and able to follow all study procedures and assessments according to the study protocol
16. Female patients of childbearing potential (FPCBP) or procreative male patients (PMP), willing to use highly effective contraceptive methods throughout the study duration and at least until 5 months after the last study treatment. The investigators must inform the participant about the risks not to use an effective method of birth control during the course of the study and they should discuss with the participant the most appropriate method.
 - FPCBP means female patients who are neither menopausal (for a minimum of at least 2 years), nor underwent irreversible surgical procedures leading to permanent infertility like bilateral tubal occlusion or hysterectomy;

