- Change in REMyDI myelin fraction in lesions at week 48 compared to baseline
- Change in REMyDI myelin fraction in NAWM at week 48 compared to baseline
- Change in intra-lesional axonal density at week 48 compared to baseline as measured with multi-shell diffusion
- Change in NAWM axonal density at week 48 compared to baseline as measured with multi-shell diffusion
- Change in axonal density, MTR, REMyDI myelin fraction in rim lesions (as part of slowly expanding lesions) vs non-rim lesions at week 48 compared to baseline

Study Code: GNC-401
Version No: 3.0
Version Date: 2020-05-01

- Change in levels of neurofilament-light chain protein (NfL) in serum at Week 48 compared to baseline (Day 1)
- Change in levels of neurofilament-light chain protein in CSF at Week 48 compared to baseline (Day 1)
- Change in levels of proteins or gene expression related to MS or the target of temelimab (pHERV-W ENV), in blood at Week 48 compared to Baseline and in CSF at Week 46 compared to Baseline
- Change in levels of immunoglobulin (Ig) levels in blood (including Total Ig, IgG, IgM, and IgA isotypes) at Week 48 compared to baseline (Day 1)
- Pharmacokinetics (PK) in serum of repeated doses of temelimab at Weeks 4, 24, 46 and 48
- Levels of temelimab in CSF at D15 post last study drug administration (Week 46)
- Antidrug antibodies (ADA) in serum of repeated doses of temelimab at pre dose Day 1, Weeks 4, 24, 46 and 48 (or, in case of early termination, at the study discontinuation visit)

Study period: Q2 2020 (First Patient First Visit)– Q4 2021 (Last Patient Last Visit)

2. Statistics

Statistical analysis will be performed by eXYSTAT SAS. A Statistical Analysis Plan (SAP), and associated templates for Tables, Listings and Figures, will be written and signed before the database lock and study unblinding. These specifications will detail the implementation of all the planned statistical analyses in accordance with the main characteristics stated in this protocol.

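### The PK plan describes CSF and serum levels by dose group only; naming a within-patient CSF:serum ratio and a proportionality slope, each with an interval, would answer its own questions better at little cost

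*Combined protocol and SAP*

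**What the plan says.** The Synopsis lists, among the exploratory objectives, "To determine the PK characteristics of temelimab following repeated IV administration (including CSF distribution) and immunogenicity". The exploratory endpoints include "Pharmacokinetics (PK) in serum of repeated doses of temelimab at Weeks 4, 24, 46 and 48" and the CSF level of temelimab at Week 46, 15 days after the last infusion by the protocol's day count. Inclusion criterion 14 reads "Agreeing to undergo two lumbar puncture", so CSF is intended from every patient. Allocation is 1:1:1:1 among 40 patients, that is 10 on placebo and 10 on each of 18, 36 and 54 mg/kg.

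The analysis is in section 10.2.5.1 (PK interpretation). Cmin and an accumulation factor are given as examples of the parameters to be derived. On proportionality: "The PK parameters will be described by treatment groups to make an initial assessment of dose linearity/proportionality". On the summaries: "Descriptive statistics (mean, standard deviation, median, min, max, variation coefficient) will be performed on CSF and serum concentrations of temelimab and PK parameters". Individual listings and individual and group plots are added, and a further population PK analysis is foreseen without a model, a CSF component or a target parameter. The visits that form the accumulation factor are not stated.

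**The concern.** Two questions are posed: how much temelimab reaches the CSF relative to serum, and whether exposure rises in proportion to dose. Each is a question about a relation, between two fluids in one patient or between exposure and dose. The stated analysis describes each quantity group by group and leaves the relation to the eye.

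If Week 46 CSF levels turn out low or variable, by-dose summaries cannot separate low serum exposure from poor passage into the CSF. A within-patient ratio can. That matters because the Synopsis places the drug's postulated targets, microglia and oligodendrocyte precursor cells, in the central nervous system. For proportionality, three group summaries do not show how large a departure the data could rule out.

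Other sections do not fill the gap. Section 2.2.1 promises estimates with 95% CIs for temelimab against placebo, and section 10.2.5.2 applies a change-from-baseline ANCOVA and the Bayesian methods to the exploratory endpoints. Neither suits a drug concentration, which is expected to be absent at baseline and on placebo.

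**Working it through.** The documents give no PK precision figure to reproduce. Section 2.3 says that N=40 does not rest on a formal statistical assessment, and Table 3 concerns MTR. The check is therefore whether the data allow the direct estimates, and how precise they would be.

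**Schedule.** Infusions every 4 weeks from Week 0 to Week 44 make 44/4 + 1 = 12, as stated. Week 44 plus 14 days is Week 46, or D15 if the infusion day is D1. Serum and CSF thus share a nominal week; clock times are not given.

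**Assumptions.** Log-normal concentrations, with log-SD s = √ln(1+CV²). For CV 30, 40 and 60%, s = 0.294, 0.385 and 0.555. These CVs are assumed, because the documents give none.

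**Proportionality slope.** Model: ln(Cmin) = a + b·ln(dose), where b = 1 is proportionality.
- ln(18), ln(36), ln(54) = 2.890, 3.584, 3.989; mean 3.488.
- Sxx = 10 × (0.357 + 0.009 + 0.251) = 6.17.
- SE(b) = s/√6.17 = 0.118, 0.155, 0.223.
- 90% half-width = t(0.95; 28 df) × SE = 1.701 × SE = 0.20, 0.26, 0.38.
- With 8 evaluable patients per dose: 0.23, 0.30, 0.43.

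**Week 46 CSF:serum ratio.** The 95% CI of the geometric mean is ×/÷ exp(t·s/√n), with s from the CV of the ratio. Pooled over 30 patients, with 27 df (variance within dose), t = 2.052:
- CV 30%: exp(2.052 × 0.294/5.477) = 1.12
- CV 40%: exp(2.052 × 0.385/5.477) = 1.16
- CV 60%: exp(2.052 × 0.555/5.477) = 1.23

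**How much comes from pairing and how much from pooling.** Take serum CV 40% and, independent of it, ratio CV 40%. The CSF log-variance is then 0.148 + 0.148 = 0.297, so s = 0.545.

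| Quantity | n | 95% CI |
|---|---|---|
| CSF level, one dose | 10 | ×/÷1.48 |
| Ratio, one dose | 10 | ×/÷1.32 |
| Dose-normalised CSF, pooled | 30 | ×/÷1.23 |
| Ratio, pooled | 30 | ×/÷1.16 |

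On the log scale, pairing alone cuts the half-width from 0.39 to 0.28, and pooling alone cuts it to 0.20. Pooling does more.

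**Dependence on correlation.** The setting above implies a serum-CSF log correlation of 0.385/0.545 = 0.71. If serum and CSF both have CV 40% and correlation ρ, the log-SD of the ratio is √(2 × 0.148 × (1−ρ)): 0.39 at ρ = 0.5, 0.46 at 0.3 and 0.54 at 0, against 0.39 for CSF alone. At ρ = 0.5 the ratio is no more precise than the CSF level, and below that it is less precise.

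**Accumulation factor.** If each of the two samples carries independent log-normal within-patient noise, the arithmetic mean of the ratios is inflated by 1+CV²: 4, 9, 16 and 25% at within-patient CV 20, 30, 40 and 50%. The median and the geometric mean are not inflated.

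**The case against.** The strongest reply is that the plan does what it promises. PK is an exploratory objective, only an initial look at proportionality is announced, and no decision, error rate or sample size depends on a PK interval. The parameter list is given by example, individual plots are planned, and population PK could estimate dose linearity and perhaps CSF partition. Section 2 leaves detail to a SAP signed before database lock, and it refers to a section 4.3 that is not in the text available, so more may be written elsewhere. The ratio can be derived from the planned data at any time, so no information is lost.

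Most of this stands, and it sets the severity. What it does not do is name an estimand: an open list commits to nothing, and the population PK sentence narrows the gap without closing it. A slope with an interval is still an initial assessment, and a half-width of ±0.38, though wide, tells the reader what three doses of 10 can support.

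Stronger readings are tempting but not supported:
- **That the trial will yield no estimate of penetration or proportionality.** The text specifies none; it does not exclude one.
- **That the summaries are purely arithmetic and the accumulation factor will be biased.** The planned median avoids the inflation of the mean.
- **That the ratio narrows the interval from ×/÷1.48 to ×/÷1.16.** This sets one dose group's CSF level against a ratio pooled over three groups. The two are different quantities, and pooling accounts for more of the change than pairing.
- **That doses cannot be combined without the ratio.** Under proportionality, dose-normalised CSF levels can be pooled too.

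**Conclusion.** The point holds as a low-severity improvement to an exploratory analysis, not as an error. The case for the ratio is mainly that it answers the question asked, CSF relative to serum. Any gain in precision over CSF levels alone depends on the serum-CSF correlation, which the documents do not give. The precision figures rest on log-normality, on the assumed CVs, on full evaluability (10 patients per dose for the slope, 30 Week 46 pairs for the pooled ratio) and, for the pooled ratio, on its not depending on dose.

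**What to change.** In the SAP:

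1. Derive each temelimab patient's Week 46 CSF:serum ratio. Report the geometric mean with 95% CI by dose and, if it is similar across doses, pooled over all temelimab patients. State the number of pairs and a rule for CSF values below the assay limit, which have no usable logarithm.
2. Estimate proportionality by regressing log Cmin on log dose, and report the slope with a 90% CI beside the planned by-group summaries. State which visits supply Cmin.
3. Define the visits that form the accumulation factor and report it as a geometric mean ratio with a CI. Week 48 over Week 4 is one definition that the serum schedule allows.
4. If population PK is carried out, say whether it covers CSF and dose linearity.

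The cost is SAP wording and one derived variable, with no new samples or visits. The downside is that pooling assumes a ratio that does not depend on dose. The by-dose display checks this, though only roughly with 10 patients per dose.

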10.2.5.2 Exploratory analyses

Each exploratory endpoint will be described by treatment group in the RS population.

Same Frequentist and Bayesian methodologies will be used.

For frequentist approach change from baseline at Week 48 will be analyzed using a non-parametric ANCOVA including baseline and treatment as factors.

Time to first relapse will be analyzed by Kaplan-Meier method and the associated log-rank test.

For the number of new T2 lesions, each dose will be compared to placebo using a Negative Binomial Generalized Linear Model (NBGLM) studying treatment effect and adjusted for baseline and treatment.

Study Code: GNC-401
 Version No: 3.0
 Version Date: 2020-05-01

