2.1. Analysis population

Randomized Set (RS): All patients to whom a therapeutic treatment was randomly assigned using IRS. Patients will be analyzed in their randomization group whatever the treatment they received

Safety Set (SS): All patients having taken at least one dose of IMP. Patients will be affected to the group of treatment they received.

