2.2. Statistical methods

2.2.1. General considerations

The following descriptive statistics will be provided depending on the nature of considered data:

- **Qualitative data:** number of observed values, number and percentage of patients per class;
- **Quantitative data:** number of observed values, mean and standard deviation, median, first and

Study Code: GNC-401
Version No: 3.0
Version Date: 2020-05-01

third quartiles, minimum and maximum;

- **Survival data (time to event occurrence or to censoring):** total number of patients, total number and percentage of patients having an event, number of patients at risk, number of patients with censored data, number of patients with event of interest.

The type I error will be set at $\alpha = 5\%$ two-sided.

The treatment effect (temelimab versus placebo) will be estimated as well as its precision: estimate of the difference, standard error (SE) of the estimate and two-sided 95% confidence interval (CI) of the estimate.

In case of formal comparison between treatment groups, the two-sided p-value associated with the treatment effect will also be provided.

All inferential analyses are considered as exploratory in order to have a first estimation of treatment effect. Consequently, no method to handle with multiplicity issues is needed.

2.2.2. Study patients:

Demographic data and other baseline characteristics will be described by treatment group, to assess their comparability, and overall in the RS population. The main patients' characteristics will also be described for SS population.

Disposition of patients, including reasons for withdrawal, protocol deviations, extent of exposure and treatment compliance, as well as concomitant treatments will be described in the RS population.

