2.2.3. Safety analysis

Safety and tolerability of temelimab and placebo will be assessed in each treatment group in the safety population.

AE summaries will include all AEs starting on or after study day 1 (i.e. on the day of or following the day of first study treatment administration) and starting before the end of study visit, i.e. 4 weeks after the date of last study treatment administration.

A Summary of AEs (number and % of patients, number of AEs) and summarized by System Organ Class (SOC) and Preferred Term (PT) will be tabulated by treatment group and overall for patients with:

- at least one treatment-emergent adverse event (TEAE),
- at least one related treatment-emergent adverse event (TEAE),
- at least one severe treatment-emergent adverse event (TEAE),
- at least one severe related treatment-emergent adverse event (TEAE),
- at least one serious TEAE,
- at least one serious TEAE related to the study treatment,
- a TEAE leading to treatment discontinuation,
- a related TEAE leading to treatment discontinuation,
- a TEAE leading to death.

Study Code: GNC-401
Version No: 3.0
Version Date: 2020-05-01

AEs will be summarized by presenting the number and percentage of patients having at least one AE and by number of AEs, overall and by treatment group. Data will be presented by SOC and PT using the latest version of MedDRA. A patient with multiple occurrences of the same PT will be counted only once in the AE category.

Separate AE summaries will be presented by SOC, PT, and severity. In the summaries presented by severity, all AEs will be pooled. Specific tables will summarize related AEs to temelimab.

Written narratives will be produced for all SAEs.

Adverse events/SAEs occurring after signing the Inform Consent Form (ICF) but before starting study treatment, including those observed in patients included but never treated with the IMP, will be listed separately from those occurring after treatment start.

Adverse events/SAEs occurring after 4 weeks after the date of last study treatment administration will be also listed separately.

Laboratory data analysis:

The summaries will include all laboratory assessments collected during the study.

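### PK, CSF temelimab, ADA and extent of exposure fall in the as-randomised set; these summaries should be grouped by treatment actually received

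*Combined protocol and SAP*

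**What the plan says.** Section 2.1 defines only two analysis sets.

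- **Randomized Set (RS).** "Patients will be analyzed in their randomization group whatever the treatment they received".
- **Safety Set.** Membership is "All patients having taken at least one dose of IMP", and for grouping, "Patients will be affected to the group of treatment they received".

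No PK set is defined. The outputs are assigned as follows.

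- **Serum PK, CSF temelimab, ADA.** All three are in the Synopsis list of exploratory endpoints; the serum item reads "Pharmacokinetics (PK) in serum of repeated doses of temelimab at Weeks 4, 24, 46 and 48". Section 10.2.5.2 then states: "Each exploratory endpoint will be described by treatment group in the RS population".
- **PK parameters and proportionality.** Section 10.2.5.1: "The PK parameters will be described by treatment groups to make an initial assessment of dose linearity/proportionality". It names no analysis set and does not mention ADA.
- **Exposure, compliance, concomitant treatments.** Section 2.2.2 (Study patients): "extent of exposure and treatment compliance, as well as concomitant treatments will be described in the RS population".
- **AEs and other safety data.** Section 2.2.3: "Safety and tolerability of temelimab and placebo will be assessed in each treatment group in the safety population". Under its heading for other safety data, the same section also covers concomitant medication, which the Synopsis lists as a primary endpoint.

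**The concern.** A serum or CSF concentration reflects the dose that was infused. Analysing by assigned group protects a randomised comparison of efficacy, but it serves no purpose for a trough concentration, an accumulation factor or a first look at proportionality over 18 to 54 mg/kg. If a patient receives another arm's treatment, RS grouping puts that patient's concentrations under the wrong dose. With 10 patients per arm, one such patient has visible weight in a group mean. ADA, which are read against the product and dose received, have the same problem.

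Extent of exposure raises a related point. A reader will naturally set the exposure table beside the AE table, and as written the two follow different grouping rules. Concomitant medication is assigned to the RS in section 2.2.2 and also falls within the safety analysis in section 2.2.3, so the plan gives that one endpoint two populations without saying which applies.

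**Working it through.** The plan states no figure to reproduce here. The check sets the sections side by side and then illustrates the size.

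**Which set applies**

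1. PK, CSF temelimab and ADA are exploratory endpoints (Synopsis).
2. Every exploratory endpoint is described in the RS (10.2.5.2).
3. The RS groups patients as randomised (2.1).
4. Section 10.2.5.1 says only that PK is summarised by treatment group. The one population rule that reaches PK and CSF levels is therefore step 2. For ADA it is the only applicable sentence.
5. Exposure is placed in the RS explicitly (2.2.2), and AEs in the Safety Set explicitly (2.2.3).

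For exposure the RS assignment is stated. For the proportionality summaries it is inferred from steps 1 and 2 together.

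**Size if a patient is misdosed**

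Inputs: 40 patients randomised 1:1:1:1 (Synopsis), so 40/4 = 10 per arm; doses 18, 36 and 54 mg/kg. Assumptions: concentration is proportional to dose, and the misdosed patient received the other dose at every infusion that affects the samples.

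*One patient assigned 18, given 54.* RS group mean, in dose units: (9 × 18 + 54)/10 = 21.6, against 18. Change: 21.6/18 − 1 = +20%.

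*One patient assigned 54, given 18.* (9 × 54 + 18)/10 = 50.4, against 54. Change: −6.7%.

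*Both together (one 18/54 swap), least-squares slope of mean ln(C) on ln(dose).*

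- x = ln 18, ln 36, ln 54 = 2.890, 3.584, 3.989; mean 3.488; deviations −0.597, 0.096, 0.501; sum of squares 0.617.
- The swap raises mean ln(C) in the 18 group by 0.1 × ln(54/18) = 0.110 and lowers it in the 54 group by the same amount.
- Slope = [0.617 − 0.110 × (0.597 + 0.501)]/0.617 = 0.80, against a true 1.00.
- Using logs of the arithmetic means (21.6, 36, 50.4) instead gives 0.77.

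*Grouped by dose received.* The slope is 1.00 by construction. With no misdosing, both groupings give the same result.

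**How likely is a deviation?** The documents give no rate. If each patient independently has probability p of receiving something other than the assigned treatment, the chance of at least one among 40 is 1 − (1 − p)^40. For assumed p of 0%, 1%, 2% and 5% this is 0%, 33%, 55% and 87%.

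**The case against.** The best case for the plan is that the harm is conditional, visible and confined to descriptive outputs. Assignment runs through an interactive response system, and no misdosing is reported. Section 10.2.5.1 is a PK subsection with its own methods. The RS sentence sits in the next subsection, ahead of covariance, Bayesian, relapse and lesion-count methods that do not suit a trough concentration, so it can be argued that the plan is silent on the PK set and has not chosen the wrong one. Medians, individual listings and plots, and an envisaged population PK analysis would expose a misplaced patient. No log-log slope is planned. The implementation detail is left to an SAP signed before database lock.

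Most of this stands, and it limits the importance of the point. It does not remove it. If 10.2.5.2 does not reach PK, then no set is defined for PK and the same wording is needed. Listings do not correct the group summaries on which proportionality is judged. The SAP is to follow the protocol's main characteristics, which currently place exploratory endpoints and exposure in the RS.

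Three stronger readings are tempting and are not supported:

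- **That the dose-AE comparison rests on mismatched groups.** AE tables are all in the Safety Set by treatment received, and no exposure-adjusted AE rate is planned. Only an informal reading of AEs beside the exposure table mixes groupings.
- **That a never-dosed patient would pull a group's mean concentration down.** That needs a zero to be imputed. The plan summarises observed values and states no such imputation.
- **That missed infusions are part of this defect.** A patient who misses an infusion stays in the same dose group under either set.

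**Conclusion.** The point holds and is minor. As written, PK, CSF temelimab and ADA fall under as-randomised grouping (by inference for the proportionality summaries), and extent of exposure does so explicitly. None of them is assigned to a set grouped by treatment received. Concomitant medication has two populations that need reconciling.

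The consequence depends on a patient receiving another arm's treatment. On the proportionality assumption with 10 per arm, a single 18-to-54 error shifts the lowest dose group's mean by 20%, and one 18/54 swap would suggest a less than proportional rise (slope about 0.80) where the truth is proportional. If everyone receives the assigned treatment, no patient changes group. The between-dose AE comparison and the power figures in section 2.3 are unaffected.

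**What to change.** - **Section 2.1:** add a PK set, made up of Safety Set patients with at least one temelimab infusion and an evaluable sample, grouped by dose received.
- **Section 10.2.5.1:** name the PK set for serum PK, CSF levels and the proportionality summaries.
- **Section 10.2.5.2:** exempt PK, CSF levels and ADA from the RS sentence. Describe ADA in the Safety Set by treatment received, keeping placebo patients.
- **Section 2.2.2:** present extent of exposure and concomitant medication in the Safety Set, in addition to the RS or in its place, so that they share groups and denominators with the AE tables. This also settles which population applies to concomitant medication.
- **Imaging and clinical endpoints:** keep the RS.

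The cost is wording and possibly two extra tables. No new data are needed, and sample size and power do not change.
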